4.6 Concomitant Therapy

All concomitant medications and treatments (including over-the-counter or prescription medicines, vitamins, vaccines and/or herbal supplements) must be recorded in the eCRF and medical records. Details regarding all prior anticancer treatment will also be recorded in the eCRF and medical records.

Any medication received within 28 days before the first dose of study treatment and within 30 days after the last dose of study treatment, or until the patient begins a new anticancer therapy, whichever occurs first, will be recorded in the eCRF and medical records. Any addition, deletion or change in the dose of these medications will also be recorded. Details of prior antineoplastic treatments including number of prior metastatic regimens will also be recorded.

Unless specifically prohibited, concomitant medications may be administered at the Investigator's discretion to manage the patient's medical condition and to conform to standard practice during the Treatment Period.

Any medication or vaccine (including over-the-counter or prescription medicines, vitamins and/or herbal supplements) that the patient is receiving at the time of enrollment or receives during the study must be recorded along with:

- a. Reason for use.
- b. Dates of administration including start and end dates.
- c. Dosage information (using generic drug names when possible), including dose and frequency.

Immunotherapy

Nivolumab and Ipilimumab are monoclonal antibodies that are cleared by catabolic processes and do not have drug-drug interaction guidelines.

Targeted therapy

Encorafenib

Encorafenib is a reversible inhibitor of CYP2B6, CYP2C9, CYP3A4 and UGT1A1. It is also a time-dependent inhibitor of CYP3A4 and induced CYP2B6, CYP2C9 and CYP3A4 in human primary hepatocytes. Permitted medications to be used with caution in this study include those that are sensitive substrates of CYP2B6, CYP2C9, CYP3A4 and UGT1A1 or those substrates that have a narrow therapeutic index.

There is a potential for encorafenib to induce CYP3A4, which may reduce the effectiveness of hormonal contraception methods. Therefore, the use of at least 1 form of non-hormonal contraception is required for females of childbearing potential during participation in this study. Caution should be used in patients receiving concomitant treatment with other drugs that are substrates of CYP3A4 as the efficacy of these drugs could be reduced when administered with encorafenib.

Encorafenib has been identified as being metabolized by CYP3A4 and to a lesser extent by CYP2C19 in vitro. Concomitant use of moderate CYP3A4 inhibitors should be avoided. If use of a moderate CYP3A4 inhibitor is unavoidable, short-term use (≤ 30 days) following discussion with the Sponsor may be permitted with an accompanying dose reduction to one-half of the encorafenib dose prior to use of the moderate CYP3A4 inhibitor. After the inhibitor has been discontinued for 3 to 5 elimination half-lives, resume the encorafenib dose that was taken prior to initiating the CYP3A4 inhibitor.

Investigators should use caution when administering encorafenib with concomitant medications with a known, conditional or possible risk to prolong the QT interval and/or induce torsade de pointes. Patients receiving such medications must be carefully monitored for potentiating of toxicity due to any individual concomitant medication and may require dose titration of the concomitant medication.

Binimetonib

In vitro, binimetonib has been identified to be primarily metabolized by glucuronidation. Strong inducers of UGT1A1 should be taken with caution when co-administered with binimetonib.

For tabulated CYP substrates, inhibitors and inducers to be used with caution or avoided, please consult the FDA website: Drug Development and Drug Interactions: Table of Substrates, Inhibitors and Inducers.

4.7 DLT

DLT-evaluable participants will be defined as participants who in the DLT evaluation period received $\geq 66\%$ of encorafenib and/or binimetonib doses and at least one dose each of nivolumab and ipilimumab.

For Cohort 1, encorafenib and nivolumab and ipilimumab will be administered on day 1 week 1. The DLT evaluation period will extend from day 1 of week 1 to the end of week 6 and captured in the medical records.

For Cohort 2, encorafenib, binimetonib, nivolumab and ipilimumab will be administered on day 1 week 1. The DLT evaluation period will extend from day 1 week 1 to the end of week 6 and captured in the medical records.

DLT Definition: A DLT is defined as any AE or laboratory abnormality that is not explained by underlying disease, disease progression, intercurrent illness, or concomitant therapies that either meets the criteria described below or results in the inability to tolerate at least 66% of the planned dose of encorafenib +/- binimetonib and at least one dose each of nivolumab and ipilimumab during Cycle 1. CTCAEv5 will be used for grading.

Dose delay criteria apply for all drug-related AEs (regardless of whether or not the event is attributed to nivolumab, ipilimumab, encorafenib, or binimetonib. If investigator can

Phase I/II study of encorafenib and binimetinib with nivolumab and low dose ipilimumab in metastatic *BRAF* mutant melanoma

attribute AE to either targeted or immunotherapy, may hold one and continue the other, otherwise delaying all study drugs is appropriate.

Specific DLT Criteria

Hematologic

- Grade 4 anemia
- Grade 4 neutropenia (for > 7 consecutive days) or Grade 4 febrile neutropenia
- Grade 4 thrombocytopenia (of any duration).
- Grade 3 thrombocytopenia with clinically significant bleeding regardless of duration or requirement of platelet transfusion

Pancreas

- Symptomatic serum amylase or lipase elevation, medical intervention required (pancreatitis Grade 3 or higher)

Gastrointestinal disorders

- Nausea and vomiting \geq Grade 3 for > 3 days despite optimal anti-emetic therapy
- \geq Grade 3 diarrhea for > 5 days despite optimal antidiarrheal treatment (which could include steroids).

Hepatobiliary

- Total bilirubin Grade \geq 4
- For participants with normal baseline AST and ALT values
 - AST or ALT >8 x ULN
- For participants with normal baseline AST and ALT and normal baseline bilirubin value:
 - AST or ALT $> 3.0 \times$ ULN combined with total bilirubin $> 2.0 \times$ ULN without evidence of cholestasis
- For participants with abnormal baseline AST or ALT or abnormal baseline bilirubin value:
 - [AST or ALT $> 2 \times$ baseline AND $> 3.0 \times$ ULN] OR [AST or ALT $> 8.0 \times$ ULN], combined with [TBIL $> 2 \times$ baseline AND $> 2.0 \times$ ULN] without evidence of cholestasis

Hypertension

- \geq Grade 3 hypertension related to the study medication if it persists > 7 days despite optimal anti-hypertensive treatment

Phase I/II study of encorafenib and binimetinib with nivolumab and low dose ipilimumab in metastatic *BRAF* mutant melanoma

- Grade 4 hypertension of any duration

Cardiac

- \geq Grade 3 cardiac event that is symptomatic or requires medical intervention

Pneumonitis

- Grade 2 pneumonitis if it persists > 7 days despite treatment with corticosteroids
- \geq Grade 3 pneumonitis of any duration

Immune-related Toxicities (except pneumonitis)

- Grade 3 immune-related toxicities that persist > 14 days with same severity despite treatment with corticosteroids.
- Grade 4 immune related toxicities of any duration \geq Grade 3 infusion related reaction

Eye disorders – Retinal

- Retinopathy or retinal detachment Grade ≥ 3 , confirmed by ophthalmic examination
- Retinal vascular disorder including RVO, confirmed by ophthalmic examination

Eye disorders – Visual disturbances without ocular (retinal) changes

- Blurred vision, flashing lights, floaters: Grade ≥ 3

Eye disorders – Other (specify)

- Grade ≥ 3 for > 21 consecutive days
- Grade 4 confirmed by ophthalmic examination

Other hematologic and nonhematologic toxicities

- Any other Grade ≥ 3 AE except: a. Lymphocyte count decreased (lymphopenia) Grade ≥ 3 unless clinically significant

Renal dysfunction

- Calculated GFR decrease of 50% from baseline
- Proteinuria 24-h urine protein > 2 g/24 h

Events which will NOT be considered DLT for the purposes of this protocol:

- Clinically insignificant laboratory values \leq Grade 2. For laboratory values \geq Grade 3, the maximum allowable time limit for correction of electrolyte abnormalities to \leq Grade 1 is 72 h.
- Cutaneous squamous cell carcinoma (CuSCC), basal cell carcinoma, and new primary melanoma which are manageable with surgical excision alone

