9. On-going or use of systemic antibiotics during the preceding 2 weeks prior to enrollment
10. Known acute or chronic infection with hepatitis B or hepatitis C virus. Participants treated with curative anti-viral therapy are eligible.

11. Known history of testing positive for human immunodeficiency virus (HIV) or known acquired immunodeficiency syndrome (AIDS) even if fully immunocompetent on ART—due to the unknown effects of HIV on the immune response to combined nivolumab plus ipilimumab or the unique toxicity spectrum of these drugs in patients with HIV.
12. Clinically unstable thromboembolic event despite anti-coagulation. Patients on stable dosing of anti-coagulants per investigator discretion are eligible.
13. Use of herbal supplements, medications or foods that are moderate or strong inhibitors or inducers of cytochrome P450 (CYP) 3A4/5 ≤ 1 week prior to the start of study treatment (Section 4.5.1).
14. History or current evidence of retinal vein occlusion (RVO) or current risk factors for RVO (e.g., uncontrolled glaucoma or ocular hypertension, history of hyperviscosity or hypercoagulability syndromes); history of retinal degenerative disease.

3.3.3 *Phase II Group 1 Specific Criteria*

1. For Phase II Group 1 (Brain Metastases): Patients may have an ECOG status of 0–2 and IS permitted to be on corticosteroids if related to disease burden and MAY have symptomatic brain lesions as long as radiation or surgical intervention is not deemed to be urgently necessary.
 - a. Symptomatic intracranial metastases may be on steroids at a total daily dose of no higher than 4 mg of dexamethasone or equivalent that is stable or tapering for 10 days prior to first treatment,
 - b. have no immediate need for SRT or surgery (within 3 week prior to first treatment),
 - c. have had no experience of seizure within 10 days prior to first treatment.

3.3.4 *Women of Childbearing Potential*

A Women of childbearing potential (WOCBP) is defined as any female who has experienced menarche and who has not undergone surgical sterilization (hysterectomy or bilateral oophorectomy) and is not postmenopausal. Menopause is defined as 12 months of amenorrhea in a woman over age 45 years in the absence of other biological or physiological causes. In addition, females under the age of 55 years must have a serum follicle stimulating hormone, (FSH) level > 40 mIU/mL to confirm menopause.

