8.2 Endpoints

The primary endpoint is the frequency of DLTs that are classified as either possibly, probably, or definitely related to study treatment according to NCI Common Terminology Criteria for Adverse Events (CTCAE v5.0). DLTs are specified in section 4.5.2. Adverse events and DLTs will be compiled separately for each phase I cohort (triple and quadruple therapy). Any patient receiving at least one dose any of study drug will be evaluable for toxicity.

Secondary endpoints include the clinical response rates in the phase II cohorts by RECIST criteria with a lower one sided 80% confidence interval. The clinical benefit rate (rate of complete response, partial response or stable disease) will also be computed with a lower one-sided confidence bound for the symptomatic brain metastasis group. Both clinical response and clinical benefit rates will apply to evaluable patients defined as having completed 4 weeks of therapy.

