8.3 Sample Size Considerations

Twelve patients will be evaluated in each phase I cohort; 30 patients will be evaluated for clinical response and clinical benefit in each phase II cohort. The total enrollment, in the absence of early stopping, is 84 patients (24 phase I / 60 phase II). Inference regarding safety of each cohort will depend upon the proportion of patients with DLT. An upper 90% confidence bound on these estimates can be used as a “rule out” criteria by the investigator such that any an unacceptably high DLT rate that is greater than the upper confidence interval may be ruled out.

Table 8.1 Upper Confidence Bounds for DLT Rate

Number of DLTs Among 12 Treated	Upper Bound of 90% Confidence Interval (%)
0	17
1	29
2	39
3	48
4	56
5	64
6	71
7	78
8	85
9	90
10	95
11	99
12	100

For example (see table 8.1), if none of 12 patients have a DLT one could claim the DLT rate is no higher than 17%, If 6 of 12 patients have treatment-related DLT the upper confidence bound is 71%, that is, the observed data (6/12) is consistent with a rate up to but not higher 71% . thus, one can rule out a DLT rate of 72% or greater.

Phase II cohorts will be used to (1) further refine the safety profile by re-estimating the DLT rate and (2) providing a preliminary estimate of efficacy.

While the phase II cohorts are accruing, The DLT rate will be continuously monitored and the trial will be suspended if the DLT rate appears to be too high. We assume, a priori, the DLT rate is thought to be 50%. A continuous monitoring program will be implemented to

detect if this assumption is an underestimate such that the rate were actually 60% or higher. Beginning with the 5th patient, continuous Bayesian monitoring calculates the probability that the DLT rate is too high and provides a stopping rule. We assume a prior

DLT probability of 50% and that the prior probability has a beta distribution with parameters 1.5 and 1.5, producing a mean of .5. As each evaluable patient is evaluated for DLT, accumulated data is used to derive the posterior probability. If the posterior probability of a DLT rate of 60% is 50% or greater, the stopping rule in the table is triggered.

The following tables provides rules for suspending the trial if the actual rate is as high as 60%:

Table 8.2 DLTs Triggering Trial Suspension at 60%

Number of Evaluable Patients (Inclusive)	Suspend if there are This many DLTs	Number of Evaluable Patients (Inclusive)	Suspend if there are This many DLTs
0-4	-----	17	11

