5-6	4	18-19	12
7	5	20-21	13
8-9	6	22	14
12	8	23-24	15
13-14	9	25-26	16
15-16	10		

For example, if 6 DLTs are observed among the first 9 patients the stopping rule for 60% DLT is enacted to signal trial suspension. The accumulated toxicities will then be evaluated by the Data and Safety Monitoring Committee for further action.

Inference from a complete 30 patient expansion cohort.

If either of the expansion cohorts runs to completion without stopping due to excess toxicity, confidence intervals can be used for inference. First, to rule out excess toxicity, an upper 90% one-sided confidence intervals (table 8.3) provides an upper bound to the DLT rate (analogous to the phase I approach). Secondly, a lower 80% one-sided confidence bound (table 8.4) can be used to rule out an ineffective regimen. (A narrower, 80% bound is used here since we want a decision that is only suggestive rather than definitive).

Table 8.3 Upper Confidence Bounds for DLT Rate

Table 8.4 Lower Confidence Bounds for Response

Number of DLTs Among 30 Treated	Upper Bound of 90% Confidence Interval (%)
0	7%
1	12%
2	17%
3	21%
4	25%
5	29%
6	32%
7	36%
8	40%
9	43%

10	46%
11	50%
12	53%
13	57%
14	60%
15	63%

Operating characteristics of possible decision rules in phase II

If a 30-patient phase II cohort is completed the following decisions are possible:

If 23 or more DLTs are observed among 30 patients the combination can be considered as too toxic and a DLT rate of 75% or greater cannot be ruled out. The probability of 23 or more DLTs with a 75% DLT rate is 92%. If the actual rate is 40% or less, the probability of 14 or fewer DLTs is 82%

Number of Responses Among 30 Treated	Lower Bound of 80% Confidence Interval (%)
0	0%
1	0%
2	3%
3	5%
4	8%
5	10%
6	13%
7	16%
8	19%
9	22%
10	25%
11	28%
12	31%

Considering a preliminary assessment of efficacy, three or fewer objective responses will suggest lack of efficacy with a response rate no better than 5%. The probability of observing 3 or fewer responses when the actual rate is 5% is 94%. However, if the actual response rate is 20% the probability of 4 or more responses is 87%.

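### The DLT-evaluable set in Section 4.7 is defined by exposure alone, so read literally it omits some patients who had a DLT, and no section names the set that governs the DLT rate

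*Combined protocol and SAP*

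**What the plan says.** Section 4.7 opens with an exposure test: "DLT-evaluable participants will be defined as participants who in the DLT evaluation period received" at least 66% of encorafenib and/or binimetinib doses and at least one dose each of nivolumab and ipilimumab. The window is weeks 1 to 6. The DLT definition that follows includes any qualifying event that "results in the inability to tolerate at least 66% of the planned dose of encorafenib", with or without binimetinib, and the minimum immunotherapy dosing.

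Section 8.2, in the paragraph that defines the primary endpoint, uses a wider set: "Any patient receiving at least one dose any of study drug will be evaluable for toxicity". Section 8.3 uses two words for the denominator. Table 8.1 is headed "Number of DLTs Among 12 Treated" and Table 8.3 also counts treated patients. The Phase II monitoring text reads "As each evaluable patient is evaluated for DLT, accumulated data is used to derive the posterior probability", and Table 8.2 counts evaluable patients. Section 8.4 refers only to the proportion of patients with a DLT.

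Three rules use the DLT rate:
- The RP2R criterion (Section 8): at least 10 patients evaluated and a DLT rate below 60%.
- The 75% criterion (Synopsis, Analyses): the investigator may declare the regimen safe if the one-sided upper 90% bound is below 75%.
- The Phase II suspension rule (Section 8.3 and Synopsis).

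**The concern.** A patient who stops early because of toxicity is the clearest example of a DLT. Under the exposure limb of 4.7 that patient has a DLT, and under the evaluability sentence of the same section the patient is not DLT-evaluable. If the evaluability sentence governs, the observed rate falls because of the events it is meant to count.

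The loss is foreseeable. Section 4.7 regards delaying all study drugs as appropriate when an event cannot be attributed. Section 4.10 requires discontinuation for some events that are also DLTs, such as AST or ALT above 8 x ULN.

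At stake is the denominator of the primary endpoint. In an open-label trial it should be settled before DLT counts are known, because the choice can move a cohort across a stated criterion.

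**Working it through.** **Reproducing the plan's figures.** The exact one-sided upper 90% bound for x DLTs in n patients is U(x, n) = the 0.90 quantile of Beta(x+1, n-x). For n = 12 it gives U(4) = 55.9%, U(6) = 71.2% and U(7) = 78.1%. Table 8.1 prints 56, 71 and 78. All 13 rows agree within rounding.

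**Who could be dropped.** Six weeks is 42 daily encorafenib doses, and 0.66 x 42 = 27.7. A patient falls below the threshold on that drug with fewer than 28 doses, so one fully dosed through day 28 cannot be dropped on encorafenib. In Cohort 2, if both drugs must meet the threshold, 0.66 x 84 = 55.4, so fewer than 56 binimetinib doses would also drop a patient.

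**Single cohorts, 12 treated, DLT patients removed from numerator and denominator.** All x from 0 to 12 were checked with one or two removed.

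| Treated | Removed | Result | Rate | Upper bound | Below 75%? |
|---|---|---|---|---|---|
| 7/12 | 0 | 7/12 | 58.3% | 78.1% | no |
| 7/12 | 1 | 6/11 | 54.5% | 75.95% | no |
| 7/12 | 2 | 5/10 | 50.0% | 73.3% | yes |

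The last row is the only reversal on the 75% criterion. There is none on the <60% rule: 8/12 (66.7%) with two removed is 6/10, exactly 60.0%, which still fails.

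**Probability of a bound below 75%.** Let X ~ Bin(12, p) be the DLTs and D ~ Bin(X, f) the DLT patients below the exposure threshold. A cohort passes if U(X-D, 12-D) < 75%. The documents attach no minimum n to this criterion. The share f is an assumption.

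| True rate p | f = 0 | 10% | 25% | 50% |
|---|---|---|---|---|
| 60% | 33.5% | 36.9% | 46.7% | 62.8% |
| 75% | 5.4% | 7.0% | 11.7% | 22.7% |

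If dropped patients were instead replaced until 12 were evaluable, the apparent rate would be p(1-f)/(1-pf). For p = 60% that is 57.4%, 52.9% and 42.9%, with pass probabilities of 40.4%, 53.1% and 78.7%. For p = 75% the pass probabilities are 7.6%, 13.0% and 33.5%. The plan has no replacement rule.

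**RP2R criterion, same model without replacement.** This rule does require 10 patients. At p = 60% the chance of meeting it falls from 56.2% to 55.2%, 46.4% and 20.5%, because only 96.8%, 73.6% and 25.3% of cohorts keep 10. Here the literal reading makes the rule harder to meet.

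**Phase II suspension.** With the Beta(1.5, 1.5) prior, the posterior probability of a rate above 60% is 0.589 at 6/9 and 0.491 at 5/8, against a trigger of 0.50. This matches the plan's example, "if 6 DLTs are observed among the first 9 patients the stopping rule for 60% DLT is enacted to signal trial suspension". If one of those six DLT patients were not evaluable, the count would be 5/8, where Table 8.2 requires 6.

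**Choice of set without any DLT patient being lost.** 6/12 has bound 71.2% and passes. If one of the 12 was under-exposed without a DLT and is excluded, 6/11 has bound 75.95% and fails.

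**The case against.** Section 8 does lean towards treated patients. The any-dose sentence stands in the endpoint paragraph, and Tables 8.1 and 8.3 count treated patients. Section 8.3 has 12 evaluated per cohort and 24 enrolled, which fits best if every treated patient counts. The term DLT-evaluable never appears in Section 8. The literal reading would also make the exposure limb of 4.7's own DLT definition largely inoperative, so it is probably not what was meant. This stands as evidence of intent, but it is not a stated rule. It leaves the 4.7 definition without a use, the RP2R rule's minimum of 10 evaluated suggests that not all 12 need count, and the suspension rule uses *evaluable*. The other definitions of that word, in 8.2 and 8.4, concern response.

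A reader might infer more than the documents support:
- *That a toxic regimen would be declared safe.* Neither Phase I criterion is automatic: one is a permission to the investigator, and RP2R selection includes review of all clinical data.
- *That the any-dose set biases the rate by dilution.* DLTs per treated patient is a legitimate estimand. It differs from DLTs per adequately exposed patient and is not an error.
- *That a trigger would be lost.* Monitoring is continuous, so a boundary missed at one patient may be reached at a later one. The Synopsis table also has different boundaries (8 DLTs at n = 9), under which 6/9 does not suspend. The two tables must be reconciled, and this point does not say which is right.
- *That DLTs are undefined because of "DLTs are specified in section 4.5.2".* This looks like old numbering. Exclusion 13 likewise points to a missing section ("1 week prior to the start of study treatment (Section 4.5.1") for CYP content now in 4.6. The DLT criteria are in 4.7, but the reference does not settle the denominator.

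**Conclusion.** The point holds as an internal contradiction in the definition behind the primary endpoint. Section 4.7, followed literally, removes patients whom the same section says had a DLT, and no section states which set governs the DLT rate. It should be fixed, but its size is modest. One or two dropped DLT patients in 12 change one outcome on the 75% criterion and none on the <60% rule. Larger shifts, such as 33.5% to 62.8% at a true 60%, need half of all DLT patients to fall below the exposure threshold. The documents give no figure for that share, so every probability for f above zero is illustrative. The one-patient example (6/12 against 6/11) shows why the set must be fixed in advance even if nobody intends to drop a DLT patient.

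**What to change.** In 4.7, extend the DLT-evaluable definition to include any treated patient who had a DLT in the 6-week window. Alternatively, state that the any-dose set of 8.2 is the DLT denominator. Either way every patient with a DLT is counted. Then name that one set in 8.2 to 8.4 for the DLT rate, the RP2R and 75% criteria and the Phase II suspension rule, align the table labels, and compute the bound at the actual n. Correct the 4.5.2 references in 8.2 and 8.4 to 4.7 in the same edit.

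The cost is a few sentences. If the exposure-or-DLT set is chosen, a cohort may have fewer than 12 evaluable patients, and Table 8.1 then needs rows for n = 10 and 11. The any-dose option avoids this, but it counts under-exposed patients without a DLT, and the plan should say that this is intended.

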4.5 Selection and Timing of Dose for Each Subject

Dosing and schedules for QUAD-01 are outlined in Table 4.5A and 4.5B. The investigational products nivolumab at 3mg/kg and ipilimumab at 1mg/kg will be given every 3 weeks for the first 4 treatments, then switched to single agent nivolumab at 480mg flat dose for up to one year. Encorafenib with or without binimatinib will be dosed as shown in Table 4.5A.

Table 4.5A: Dosing Schedule for Phase I

	Day 1 Week 1	Day 1 Week 2	Day 1 Week 3	Day 1 Week 4	Day 1 Week 5	Day 1 Week 6	Day 1 Week 7
Cohort 1: Triple therapy (encorafenib + nivolumab + ipilimumab)	300 mg encorafenib PO daily						
	3mg/kg Nivolumab			3mg/kg Nivolumab			3mg/kg Nivolumab
	1mg/kg Ipilimumab			1 mg/kg Ipilimumab			1 mg/kg Ipilimumab
Cohort 2: Quadruple therapy (encorafenib + binimetinib + nivolumab + ipilimumab)	450 mg encorafenib PO daily						
	45 mg binimetinib PO BID						
	3mg/kg Nivolumab			3mg/kg Nivolumab			3mg/kg Nivolumab
	1mg/kg Ipilimumab			1 mg/kg Ipilimumab			1 mg/kg Ipilimumab

*Investigational products nivolumab and ipilimumab will be administered every 3 weeks for the first four doses, then single agent nivolumab will be administered every 4 weeks at flat dose of 480mg for up to one year.

Phase I/II study of encorafenib and binimetinib with nivolumab and low dose ipilimumab in metastatic *BRAF* mutant melanoma

Table 4.5B: Dosing Schedule for Phase II

	Day 1 Week - 2	Day 1 Week - 1	Day 1 Week 1	Day 1 Week 2	Day 1 Week 3	Day 1 Week 4	Day 1 Week 5
Group 1: Brain metastases	RP2R	RP2R	RP2R	RP2R	RP2R	RP2R	RP2R
Group 2: Elevated LDH OR Bulky Visceral Disease SLD > 44 mm	RP2R	RP2R	RP2R	RP2R	RP2R	RP2R	RP2R

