4.10 Guidelines for Permanent Discontinuation

- Any Grade 2 drug-related uveitis or eye pain or blurred vision that does not respond to topical therapy and does not improve to Grade 1 severity within the re-treatment period OR requires systemic treatment
- Any Grade 3 non-skin, drug-related AE lasting > 7 days, with the following exceptions for laboratory abnormalities, drug-related uveitis, pneumonitis, bronchospasm, hypersensitivity reactions, infusion reactions, and endocrinopathies:
 - Grade 3 drug-related uveitis, pneumonitis, bronchospasm, hypersensitivity reaction, or infusion reaction of any duration requires discontinuation
 - Grade 3 drug-related endocrinopathies adequately controlled with only physiologic hormone replacement do not require discontinuation
 - Grade 3 drug-related laboratory abnormalities do not require treatment discontinuation except:
 - ◆ Grade 3 drug-related thrombocytopenia > 7 days or associated with bleeding requires discontinuation
- Any drug-related liver function test (LFT) abnormality that meets the following criteria require discontinuation:
 - AST or ALT > 8 x ULN
 - Total bilirubin > 5 x ULN
 - Concurrent AST or ALT > 3 x ULN and total bilirubin > 2 x ULN
- Any Grade 4 drug-related AE or laboratory abnormality, except for the following events which do not require discontinuation:
 - Grade 4 neutropenia ≤ 7 days
 - Grade 4 lymphopenia or leukopenia
 - Isolated Grade 4 amylase or lipase abnormalities that are not associated with symptoms or clinical manifestations of pancreatitis. The Study PI should be consulted for Grade 4 amylase or lipase abnormalities.
 - Isolated Grade 4 electrolyte imbalances/abnormalities that are not associated with clinical sequelae and are corrected with supplementation/appropriate management within 72 hours of their onset

Phase I/II study of encorafenib and binimetinib with nivolumab and low dose ipilimumab in metastatic *BRAF* mutant melanoma

- Any event that leads to delay in dosing lasting > 6 weeks from the previous dose requires discontinuation, with the following exceptions:

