9.2.2 Study Drug Records

It is the responsibility of the investigator to ensure that a current disposition record of study drug (inventoried and dispensed) is maintained at the study site to include investigational product and the following non-investigational product(s): ipilimumab. Records or logs must comply with applicable regulations and guidelines and should include:

- amount received and placed in storage area
- amount currently in storage area
- label identification number or batch number
- amount dispensed to and returned by each subject, including unique subject identifiers
- amount transferred to another area/site for dispensing or storage
- non-study disposition (e.g., lost, wasted)
- amount destroyed at study site, if applicable
- amount returned to BMS
- retain samples for bioavailability/bioequivalence, if applicable
- dates and initials of person responsible for Investigational Product dispensing/accountability, as per the Delegation of Authority Form.

BMS will provide forms to facilitate inventory control if the investigational site does not have an established system that meets these requirements.

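### The evaluability and tolerance rules in section 4.7 do not fit together, so some drug-related intolerance can be left out of the DLT rate

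*Combined protocol and SAP*

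**What the plan says.** Section 4.7 has two sentences that decide how a patient enters the DLT rate.

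- **Evaluability.** A patient counts if, in the DLT evaluation period, they received at least 66% "of encorafenib and/or binimetonib doses and at least one dose each of nivolumab and ipilimumab".
- **Tolerance.** Apart from the listed criteria, a DLT is also an "inability to tolerate at least 66% of the planned dose of encorafenib +/- binimetonib". The infusion part of this clause reads: "and at least one dose each of nivolumab and ipilimumab during Cycle 1".

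For Cohort 2 the same section says: "The DLT evaluation period will extend from day 1 week 1 to the end of week 6". Cohort 1 has the same window. Under section 4.5 nivolumab and ipilimumab "will be given every 3 weeks for the first 4 treatments", and Table 4.5A places them in weeks 1, 4 and 7. Section 4.3 gives encorafenib once daily and binimetinib twice daily, both continuously.

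Section 8.2 makes the DLT frequency the primary endpoint, compiled separately for the triple and quadruple cohorts. It counts anyone who received a dose of any study drug as evaluable for toxicity. Section 4.10 requires permanent discontinuation for "Any Grade 3 non-skin, drug-related AE lasting > 7 days", with listed exceptions. The immune-related line in section 4.7 counts a Grade 3 event only if it persists beyond 14 days.

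**The concern.** The tolerance clause is there to catch patients who cannot stay on the regimen although no listed criterion is met. As written it can miss some of them, and the evaluability sentence can remove others from the denominator. The DLT rate informs the choice of recommended phase II regimen in section 8 (at least 10 patients evaluated, DLT rate below 60%) and the Synopsis rule that a regimen may be declared safe if the upper bound is below 75%. With 12 patients per cohort, one or two unclear classifications can move the result across either line.

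**Working it through.** **1. The plan's own figure.** The exact one-sided 90% upper bound for x DLTs among n patients is the 0.90 quantile of Beta(x+1, n−x). For n = 12 it gives 55.9% at x = 4, 63.8% at 5, 71.2% at 6, 78.1% at 7 and 84.6% at 8. Table 8.1 shows 56, 64, 71, 78 and 85, and every other entry also agrees within rounding. The table is sound; the question is what goes into its numerator and denominator.

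**2. Planned doses in the 42-day window** (sections 4.3, 4.5 and 4.7).
- Nivolumab and ipilimumab: weeks 1 and 4, so 2 doses each.
- Encorafenib: 42 × 1 = 42 doses; 66% is 27.72, so 28 doses.
- Binimetinib: 42 × 2 = 84 doses; 66% is 55.44, so 56 doses.

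**3. Infusions.** Both antibodies are given on day 1, so one dose of each is normally reached that day, at 1/2 = 50% of what is planned. Neither sentence looks at the second dose, whatever Cycle 1 means. Take a Grade 3 immune-related event of 8 to 14 days that is non-skin, outside the section 4.10 exceptions and without its own DLT line. Section 4.10 requires discontinuation because it exceeds 7 days, yet the immune line in 4.7 is not met because it does not exceed 14. If the oral treatment continues, which 4.7 allows when the event can be attributed to one drug class, the tolerance clause is not triggered either.

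**4. Binimetinib in Cohort 2.** Under and/or, 42/42 encorafenib with 0/84 binimetinib is evaluable. Appendix 3 provides for withholding binimetinib alone for up to 4 weeks after an asymptomatic fall in ejection fraction. A full 4-week hold inside the window leaves at most 28/84 = 33% of binimetinib, and the patient is still evaluable on encorafenib. If doses are pooled instead (42 + 84 = 126; 66% is 83.16, so 84), encorafenib alone is 42/126 = 33.3% and fails, while binimetinib alone is 84/126 = 66.7% and passes. The tolerance clause says +/-, which can be read as requiring binimetinib in Cohort 2. The classification depends on a reading that the plan does not state.

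**5. Window and denominator.** Cycle 1 has no stated length.

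| Patient stops the oral drug(s) because of toxicity below the listed lines | Tolerance clause | Evaluability sentence (six weeks) |
|---|---|---|
| Cycle 1 = 21 days (66% = 13.86, so 14 days); stops after 14–27 days | not a DLT | not evaluable |
| Cycle 1 = six weeks; stops before 28 days | DLT | not evaluable |

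In the first row the patient is in neither count. In the second the patient is a DLT under one sentence and excluded under the other, because evaluability has no limb for patients who had a DLT. Under section 8.2 both patients are evaluable for toxicity.

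**6. Size.** The documents give no rate for these events, so only the sensitivity can be shown. Moving one patient of 12 from tolerated to DLT has these effects:
- 4 to 5 DLTs: the bound goes from 55.9% to 63.8%, across the 60% mark that the Synopsis uses for 4 or fewer DLTs;
- 6 to 7: the bound goes from 71.2% to 78.1%, across 75%;
- 7 to 8: the observed rate goes from 58.3% to 66.7%, across the 60% criterion in section 8.

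As an assumed illustration, let the true non-tolerance rate be 60% and let all 12 patients stay in the denominator. The probability of 6 or fewer counted DLTs (bound below 75%) is 0.335 if every case is counted, 0.473 if 5 percentage points are missed, 0.613 if 10 are missed and 0.842 if 20 are missed.

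**The case against.** The strongest reply is that the listed criteria do most of the work. Section 4.7 has specific lines for Grade 3 or higher diarrhea beyond 5 days, pneumonitis, infusion reactions and transaminases above 8 times the upper limit, and a catch-all for other Grade 3 or higher events apart from lymphopenia that is not clinically significant. This stands: only Grade 2 or lower intolerance, and Grade 3 events short of a listed duration, can escape. Someone applying the catch-all broadly might capture the latter too, although it is worded for events not already listed.

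Second, +/- elsewhere denotes the triple or quadruple regimen, so losing binimetinib to toxicity may already be a DLT in Cohort 2. That is a fair reading. It means the documents do not establish that such a patient counts as tolerating quadruple therapy. What remains is that the two sentences of 4.7 differ.

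Third, a discontinuation threshold and a DLT threshold serve different purposes and need not match, and section 4.10 exempts skin events, most laboratory abnormalities and controlled endocrinopathies. This narrows the 8 to 14 day gap but does not close it.

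Fourth, the regimen is chosen after review of all clinical data, and section 8.4 tabulates toxicity by type and grade. Intolerance is therefore not hidden from the decision-makers, although it can be missing from the rate and bound on which the stated criteria rest.

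**Conclusion.** Section 4.7, read with section 8.2, does not give one unambiguous primary-endpoint rule, and some drug-related intolerance can be left out of the DLT rate. The infusion part holds on any reading of Cycle 1, barring a failed day 1 infusion. The neither-counted group of 14 to 27 days exists only if Cycle 1 means 21 days. The gap is partial and its frequency cannot be derived, but one patient in 12 can change a conclusion. This should be fixed; it does not invalidate the design.

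Three stronger readings are tempting and are not supported.
- A reader might infer that the rule tilts the choice toward quadruple therapy. The infusion and window problems affect both cohorts alike, and the binimetinib problem rests on a contested reading.
- A reader might build a case in which 7/12 (bound 78.1%) is reported as 5/10 (bound 73.3%). The bounds are correct, but the two dropped patients are an assumption. Both observed rates (58.3% and 50%) meet the below-60% criterion, and under section 8.2 the denominator would stay at 12.
- A reader might infer that oral exposure goes unrecorded, because section 9.2.2 refers to "the following non-investigational product(s): ipilimumab". That label conflicts with sections 4.1 and 4.2, but Table 4.1 lists both oral drugs as study drugs and 9.2.2 requires records of study drug. It is a minor labelling error.

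**What to change.** 1. Define a DLT-evaluable patient as one who experienced a DLT, or who received in the DLT evaluation period at least 66% of planned encorafenib (Cohort 1), or at least 66% of encorafenib and at least 66% of binimetinib (Cohort 2). The DLT limb is essential: tightening exposure alone would drop the very patients who fail to tolerate the regimen.
2. State the tolerance clause per drug in the same way, and replace Cycle 1 by the DLT evaluation period, day 1 to the end of week 6.
3. State whether the section 4.7 or the section 8.2 denominator applies to the DLT rate.
4. Report beside the DLT rate, with the same one-sided 90% upper bound, the proportion of patients who missed the second nivolumab/ipilimumab dose because of drug-related toxicity.
5. Have the investigators reconcile the duration thresholds in 4.7 and 4.10, or state why they differ. This review takes no position on which should apply.
6. Correct the non-investigational product label in 9.2.2 to agree with 4.1 and 4.2.

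The cost is wording and one extra tabulation. The downside is that the DLT or intolerance figure may look worse, and a patient who misses the 66% for reasons other than toxicity may become non-evaluable.
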